Exercise Training. For Exercise Training sessions (Exercise Training group only), subjects will report to the lab for a supervised exercise training session 3-4 times per week. Subjects will be instrumented with a heart rate monitor chest strap and heart rate will be constantly monitored during training sessions. During the first and final session of Exercise Training for each subject, core temperature will be continuously monitored and recorded using a wireless, disposable core temperature sensing pill. Exercise will consist of a 5-minute warm-up of seated upright cycling at 30% of the subject's VO_2 peak, followed by 40 minutes of cycling at 60% VO_2 peak, then a 5-minute cool down at 30%. There are some risks associated with exercise, including: light-headedness, fatigue, muscle cramps, and shortness of breath. Procedures will be terminated immediately if any subject feels light-headed, nauseated, or experiences any other adverse signs or symptoms.

1st Heat Therapy or Exercise Training Session. During the 1st heat therapy or exercise training session, we will measure the acute post-heating/exercise hypotension response. This information will be used to test the predictive power of acute post-heat/exercise hypotension on the individual response to the interventions. The subject will lay supine for 20 min of rest followed by three measures of blood pressure before the heat therapy or exercise training session. At the end of this 1st session, the subject will lay down for 1 hour of recovery, during which we will continue to monitor core temperature, heart rate, and blood pressure every 5 min.

Protocol 2:

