**Figure 1. Study Time Points**

RECRUIT
- Inactive men and women with HTN
SCREEN
- Multiple visits to assess blood pressure
PRE-TESTS
- Hemodynamic tests
- Muscle sympathetic nerve activity
- Biomarkers
- 24-h Ambulatory blood pressure
- VO 2 Peak Test
- Heat Test
ASSIGN
- Randomized to intervention group
INTERVENTION
- First 15 sessions
INTERIM-TESTS
- Hemodynamic tests
- 24-h Ambulatory blood pressure
- Biomarkers
INTERVENTION
- Last 15 sessions
POST-TESTS
- Hemodynamic tests
- Muscle sympathetic nerve activity
- Biomarkers
- 24-h Ambulatory blood pressure
- VO 2 Peak Test
- Heat Test

exercise training session. At the end of this 1st session, the subject will lay down for 1 hour of recovery, during which, we will continue to monitor core temperature, heart rate, and blood pressure every 5 min. NOTE: Subjects with contraindications for the ingestible core temp sensing pill will be encouraged to use a self-inserted rectal thermistor. If subject is contraindicated for the core temp pill and the rectal thermistor, their temperature will be monitored with a digital aural or oral thermometer.

**INTERIM-TESTS:** After half the intervention sessions have been completed, we will repeat our assessment of hemodynamic tests, 24-h urine collection and food/beverage log, 24-h ambulatory blood pressure and sleep/wake/activity log, and blood-based biomarkers related to cardiovascular health.

**POST-TESTS:** After the INTERVENTION, we will repeat high-resolution phenotyping of subjects which will include all the measures from the PRE-TESTS.

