**HEAT THERAPY VS EXERCISE TRAINING IN HYPERTENSION SAP**

dbp_dipper	Aim 1/Secondary	Categorical; non-dipper <10%, dipper ≥10% to <20%, and extreme dipper ≥20% change in diastolic BP at night calculated from ambulatory BP day and night averages
pwv	Aim 2/Primary	Continuous; average of three pulse wave velocity measurements collected at pre-, interim-, and post-intervention timepoints
il6_lg2	Aim 2/Secondary	Continuous; Biomarker IL-6 with the lower limit of detection (LLD) of 0.031 imputed for <LLD, log2 transformed for normalcy
crp_lg2	Aim 2/Secondary	Continuous; Biomarker CRP with the lower limit of detection (LLD) of 0.031 and upper LD (ULD) of 50 imputed for <LLD and >ULD, log2 transformed for normalcy
et1_lg2	Aim 2/Secondary	Continuous; Biomarker ET-1 with the lower limit of detection (LLD) of 0.031 imputed for <LLD, log2 transformed for normalcy
alb_lg2	Aim 2/Secondary	Continuous; Biomarker urine albumin with the lower limit of detection (LLD) of 0.031 imputed for <LLD, log2 transformed for normalcy
Supine.SBP.low	Aim 3/Primary	Continuous; average of three lowest consecutive supine systolic blood pressure measurements taken every 5 minutes for an hour post-intervention during supine recovery (for Heat Therapy: syst_bp55_ht_s1 to syst_bp110_ht_s1; for Exercise Training: for Heat Therapy: syst_bp55_ex_s1 to syst_bp110_ex_s1)
Supine.DBP.low	Aim 3/Primary	Continuous; average of three lowest consecutive supine systolic blood pressure measurements taken every 5 minutes for an hour post-intervention during supine recovery (for Heat Therapy: syst_bp55_ht_s1 to syst_bp110_ht_s1; for Exercise Training: for Heat Therapy: diast_bp55_ex_s1 to diast_bp110_ex_s1)
Supine.SBP.1.ch	Aim 3/Primary	Change from average pre-session resting SBP to Supine.SBP.low
Supine.DBP.1.ch	Aim 3/Primary	Change from average pre-session resting DBP to Supine.SBP.low
eGFR	Aim 1/Exploratory	eGFR was calculated using the CKD-EPI Creatinine-Cystatin Equation (2021) using the CKDEpi_RF.creat.cys function in the nephron R package and rounded to two decimal places
uacr	Aim 1/Exploratory	Urine albumin creatinine ratio (mg/g) was calculated by dividing urine albumin by urine creatinine/1000 rounded to 2 decimal places
Protocol 2		
cognitive_score	cognitive/Primary	Averaged z-scores (centered & divided by standard deviation) of age-corrected picture sequence score (age_cor_score)

		and age-corrected list-sorting score (list_age_cor_scpre)
--	--	--

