## 9 Efficacy Analyses

For primary analyses for Protocol 1 Aims 1, primary outcomes will be compared between groups (heat therapy vs exercise training) over time (within subject repeated measurements) using two-way repeated measures mixed model including an interaction between intervention group and timepoint with pre-defined contrasts. For Specific Aim 1, to test the hypothesis that heat therapy improves blood pressure (both in clinic and 24H ambulatory) better than dynamic aerobic exercise, the null hypothesis will be that the interaction between group and timepoint is equal to 0. For Aim 2, to determine whether heat therapy will improve biomarkers of arterial health (arterial stiffness & biomarkers of systemic

inflammation and oxidative stress) and compare responses to exercise training, the null hypothesis will be that the interaction between intervention group and timepoint is equal to 0. For Aims 1 and 2 exploratory analyses, ANCOVA will be performed for primary and secondary outcomes, with pretest values entered as a covariate and treatment condition specified as a fixed factor. Demographic and physiological variables (age, sex, BMI) and pre-intervention blood pressure will be added one at a time to the ANCOVAs to test for an interaction on treatment effects. For Aim 3, we will use ANCOVA models to determine the predictive potential of acute post-exercise hypotension response for chronic changes in blood pressure, with pretest values entered as a covariate and systolic and diastolic blood pressure specified as a fixed factor. Analyses will be performed on the Intention to Treat population. Additionally, change from pre- to post-intervention in ambulatory and in clinic systolic and diastolic pressure will be correlated with change from pre- to post first intervention session supine systolic and diastolic blood pressure by Pearson correlation.

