average of three consecutive readings taken every five minutes in the 55-110 minutes following the hour-long intervention. Group means for ambulatory blood pressure at the post-intervention timepoint will be estimated using the following formulas: Model 1, Post ambulatory BP ~ Pre-session BP + Intervention; Model 2, Post ambulatory BP ~ Pre-session BP + Intervention + Intervention\* Pre-session BP; Model 3, Post ambulatory BP ~ Pre-session BP + Intervention + Post-session BP + Intervention\* Post-session BP. BP measures will be included in models as continuous variables with means estimated at selected values of interaction terms to illustrate how blood pressure measures did or did not vary by subgroup. Additionally, exploratory correlations and PCA were performed among the following Project 1 variables: age, body mass index (BMI), HbA1c, total cholesterol (TC), Interleukin-6 (IL-6), C-reactive Protein (CRP), urine albumin to creatinine ratio (UACR), estimated glomerular filtration rate (eGFR), 24H ambulatory systolic and diastolic blood pressure (Amb. SBP, Amb. DBP), arterial stiffness measure pulse wave velocity (PWV), IPAQ long form continuous score MET-minutes/week (IPAQ), pre-first session resting SBP and DBP, maximum drop in supine SBP or DBP in the 55-110 minutes post-first heat or exercise session (Supine SBP or DBP drop), and total peripheral resistance (TPR), pulse wave velocity (PWV), renin, angiopoietin-2 (Ang2), endothelin-1 (Et1), and urine aldosterone.

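### Exploratory Aim 3: SAP Table 4 mixes systolic readings into the diastolic acute-response variables, and the 55 to 110 minute window in section 9.1 does not fit the one-hour recovery

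*SAP*

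**What the plan says.** **Diastolic variables (SAP 5.5, Table 4).** Four derived variables carry the acute response to the first session: Supine.SBP.low, Supine.DBP.low and the change to each from the pre-session resting value.

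- Supine.DBP.low is described in words as an average of systolic measurements. Its source fields, heat first and then exercise, are "syst_bp55_ht_s1 to syst_bp110_ht_s1; for Exercise Training: for Heat Therapy: diast_bp55_ex_s1 to diast_bp110_ex_s1".
- Supine.DBP.1.ch is defined as "Change from average pre-session resting DBP to Supine.SBP.low".
- Supine.SBP.low uses systolic fields in both arms, but its exercise fields follow a misplaced label: "for Exercise Training: for Heat Therapy: syst_bp55_ex_s1 to syst_bp110_ex_s1". The diastolic row carries the same stray label.

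**Where they are used.** Section 9 plans Pearson correlations of the pre-to-post change in ambulatory and clinic pressure with "change from pre- to post first intervention session supine systolic and diastolic blood pressure". In section 9.1, Model 3 regresses post-intervention ambulatory pressure on pre-session pressure, intervention, post-session pressure and the interaction of the last two.

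**Window.** Section 9.1 takes post-session pressure as the lowest "average of three consecutive readings taken every five minutes in the 55-110 minutes following the hour-long intervention". Its list of correlation variables again places the supine drop "in the 55-110 minutes post-first heat or exercise session". SAP 5.1 says that after the first session "the subject will lay down for 1 hour of recovery", with pressure taken every 5 minutes. Protocol section C agrees: "At the end of this 1st session, the subject will lay down for 1 hour of recovery". Table 4 also describes an hour of supine recovery.

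**The concern.** Sections 9 and 9.1 both refer to a supine diastolic change or drop, so a diastolic measure was intended. Table 4 does not define one consistently. Its wording gives systolic pressure in both arms, its fields give systolic for heat and diastolic for exercise, and the change row points to the systolic minimum.

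The field version is the more harmful because the error follows treatment. In the diastolic form of Model 3, the heat slope would be ambulatory diastolic pressure per mmHg of post-session systolic pressure, and the exercise slope would be per mmHg of diastolic pressure. Their difference would not show whether the acute response predicts differently in the two arms. In the section 9 correlations, the change variable would carry pulse pressure as well as the acute diastolic response.

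The window matters because section 9.1 tells an analyst to use readings that, taken literally, mostly do not exist. SAP section 13 logs a corrected definition of the acute reduction on 04/08/2024 and the added correlations on 05/22/24, so this is the text from which the work would be reproduced.

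**Working it through.** **1. What the change row computes.** With rest as the pre-session average:

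- intended change = DBP.low − DBP.rest
- as defined = SBP.low − DBP.rest = (DBP.low − DBP.rest) + (SBP.low − DBP.low)

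The definition therefore adds a gap of about one pulse pressure. As an illustration with assumed values, a resting DBP of 80 and a lowest SBP of 120 give 120 − 80 = +40 mmHg, an apparent rise. A constant gap would leave a Pearson correlation unchanged. Only the part of the gap that varies between participants matters.

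For that part, let s be the SD of the intended change, p the SD of the gap and r their correlation. The correlation of the literal with the intended variable is (s + r·p) / √(s² + p² + 2·r·s·p). The documents give none of these inputs. Assuming s = 3 to 5 mmHg and p = 6 to 10 mmHg:

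| r (assumed) | s = 3, p = 10 | s = 5, p = 6 |
|---|---|---|
| −0.5 | (3 − 5)/√79 = −0.23 | (5 − 3)/√31 = 0.36 |
| 0 | 3/√109 = 0.29 | 5/√61 = 0.64 |
| +0.5 | (3 + 5)/√139 = 0.68 | (5 + 3)/√91 = 0.84 |

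The range is too wide to estimate the damage. It shows only that the two variables are not interchangeable.

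**2. Readings available.** Inputs: recovery of 60 minutes with readings every 5 minutes (Protocol section C, SAP 5.1), and fields numbered 55 to 110 (Table 4).

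- Number of fields: (110 − 55)/5 + 1 = 12, and 12 × 5 = 60 minutes. Table 4 reproduces a one-hour recovery.
- Section 9.1 read literally, from session end: of 55, 60, …, 110, only 55 and 60 fall within 60 minutes. That is two readings where three consecutive ones are required.

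**3. Visit length.** Inputs: 20 minutes of supine rest; 45 minutes of immersion, or 5 + 40 + 5 = 50 minutes of cycling; Visit 6 booked for 2½ hours = 150 minutes (Protocol time-commitment table). The third row takes the session length stated in section 9.1.

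| Session | One-hour recovery | Readings to 110 minutes after session |
|---|---|---|
| Heat, 45 min | 20 + 45 + 60 = 125 | 20 + 45 + 110 = 175 |
| Exercise, 50 min | 20 + 50 + 60 = 130 | 20 + 50 + 110 = 180 |
| 60 min, per section 9.1 | 20 + 60 + 60 = 140 | 20 + 60 + 110 = 190 |

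The one-hour recovery fits 150 minutes in every row. The literal window overruns by 25 to 40 minutes.

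**4. Minute 0.** The documents do not state it. If fields are numbered from session start, exercise readings run from 55 − 50 = 5 to 110 − 50 = 60 minutes after the session. After a full 45-minute immersion they run from 55 − 45 = 10 to 110 − 45 = 65 minutes. The same field names could therefore mean different post-session times by arm.

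**The case against.** The strongest defence is that these are copying slips with an obvious intent in an exploratory aim. Table 4 gives a usable 12-field window, and nothing shows that the code followed the faulty text. That is fair. It limits the consequence but does not make the text right.

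Four stronger readings are tempting, and the documents do not support them:

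- **That the diastolic variables come wholly from systolic readings.** The exercise-arm fields are diastolic. The fault is the difference between arms and the wrong target in the change row.
- **That the offset of about one pulse pressure itself distorts the correlations.** A constant shift does not. Models 1 to 3 are also written in pre- and post-session pressure, not in the change variable.
- **That the readings were taken at the wrong times.** The fields fit the recovery hour. The conflict lies in the wording of section 9.1, and the 10 to 65 minute heat timing depends on an assumed clock.
- **That omitting pre-intervention ambulatory pressure from Models 1 to 3 is an error, or that adding it is free.** Section 9.1 names pre-session pressure as the Aim 3 covariate, which suits the stated purpose of predicting beyond baseline resting pressure. Section 9 also already correlates changes from baseline. Section 7.3 does list pre-intervention ambulatory pressure among the section 9.1 covariates, and section 9 enters pretest values for Aim 3, so the passages need reconciling. But the extra term costs one degree of freedom and may lose participants without a baseline recording. Its benefit depends on correlations the documents do not give. It would also be a change made after data were seen, since sections 8.2 and 13 show the SAP being edited during analysis.

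**Conclusion.** The point holds for two definitions in exploratory Aim 3 and should be fixed. The two diastolic rows of Table 4 are wrong as written, and the field list makes the error depend on arm. The section 9.1 window is wrong in both places: two usable readings instead of at least three, and 175 to 190 minutes against 150 booked. The counts and minutes follow from the documents alone. The effect of the diastolic error on results is unknown, and the correlation range above rests on assumed values.

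A reader might infer that reported Aim 3 results are wrong. The documents do not show this, because the code may already be correct. Aims 1 and 2 and the systolic source fields are not affected. The covariate question is an inconsistency to tidy, not an error.

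**What to change.** 1. In Table 4, define Supine.DBP.low from the `diast_bp55` to `diast_bp110` fields in both arms and describe it as diastolic. Define Supine.DBP.1.ch as the change from resting DBP to Supine.DBP.low.
2. Remove the stray heat-therapy label before the exercise fields in both the systolic and diastolic lowest-value rows.
3. Check the analysis code against the corrected rows, rerun any diastolic Aim 3 output that used the faulty ones, and log the correction with a date in section 13.
4. In both places in section 9.1, describe the window as the 12 five-minute readings of the one-hour recovery (fields 55 to 110), and state what minute 0 is in each arm.
5. Optional: reconcile the Aim 3 formulas in section 9.1 with section 7.3 and with the pretest wording in section 9. If a model with pre-intervention ambulatory pressure is added, label it post hoc and show it beside Models 1 to 3.

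Items 1 to 4 cost SAP wording and a code check, with a rerun only if the code is wrong. No new data are needed. Item 5 carries the costs noted above and is not required to correct the record.

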## 6 Sample Size

**Projected effect sizes.** To estimate effect size for the primary outcome variables of systolic and diastolic blood pressures, we bracketed over several scenarios with varying pre- to post-intervention differences (i.e., with the fall in pressure following heat therapy being 4.0, 4.5, or 5.0 mmHg greater than following exercise training), and using a SD of 4.5 mmHg from our pilot work and published studies using similar interventions and approaches, which resulted in minimum hypothesized effect sizes of 0.89, 1.00, and 1.11 for Aim 1. For MSNA, we used a pre-intervention mean value of 39 $\pm$ 7 bursts/100beats based on our pilot data with 4 HTN subjects, and determined that a post-intervention mean value of 29 $\pm$ 7 b/100bts would represent a clinically significant change (of 10 b/100bts). Thus, for MSNA,  $d = 1.43$ .

Similarly, from our pilot work and our published studies using similar interventions and approaches, calculated effect sizes for  $\beta$ -stiffness  $d = 1.43$ , DAC  $d = 1.70$ , sympathetic baroreflex  $d = 1.33$ , FMD  $d = 2.55$ , carotid wall thickness  $d = 3.33$ , for Aim 2. Effect sizes for blood pressures were the lowest of our outcome variables; thus, powering for blood pressure will allow adequate power for numerous measurements giving us a global picture cardiovascular and autonomic health.

**Statistical power.** Our prospective power estimates based on a simpler model (two-sample RCT design, modeled as a two-sample t-test), to detect a minimum hypothesized effect size of 0.89 (which is smallest effect size of interest across outcome variables; power 90%;  $\alpha=0.05$ ), indicate the need to enroll 50 subjects (50:50 ratio of study groups; sample size assumes 20% dropout for the per-protocol analysis).

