Projected effect sizes and statistical power. To estimate effect size for the primary outcome variables of systolic and diastolic blood pressures, we bracketed over several scenarios with varying pre- to post-intervention differences (i.e., with the fall in pressure following heat therapy being 4.0, 4.5, or 5.0 mmHg greater than following exercise training), and using a SD of 4.5 mmHg from our pilot work and published studies using similar interventions and approaches, which resulted in minimum hypothesized effect sizes of 0.89, 1.00, and 1.11 for Aim 1. Effect sizes for blood pressures were the lowest of our outcome variables; thus, powering for blood pressure will allow adequate power for numerous measurements giving us a global picture cardiovascular and autonomic health. Our prospective power estimates based on a simpler model (two-sample RCT design, modeled as a two-sample t-test), to detect a minimum hypothesized effect size of 0.89 (which is smallest effect size of interest across outcome variables; power 90%; $\alpha=0.05$), indicate the need to enroll 50 subjects (50:50 ratio of study groups; sample size assumes 20% dropout for the per-protocol analysis). Of those preliminarily screened who appear to be eligible, we will consent and enroll up to 250 individuals for further screening for eligibility anticipating only 50 individuals will be eligible for participation in the study. We need 50 study participants to account for rate of attrition once participants are enrolled in the formal study to ensure completion of 40 participant needed for statistical purposes.

D. Research Population, Recruitment Methods, and Compensation

Protocol 1:

The trial will be conducted in a cohort of 50 physically inactive to moderately active men and women with high blood pressure (Elevated, Stage 1, and Stage 2, based on current guidelines)⁴ from the local Eugene and Springfield, OR communities. We will attempt to recruit subjects that represent the ethnicity of Eugene, Oregon and the University of Oregon.

Subjects will be recruited locally (newspaper advertisements, flyers, radio advertisements, in-person recruitment events, online posts, as well as Craigslist and other online advertisements including ad campaigns designed and hosted by marketing companies), as well as referred to us by local physicians and clinics.

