### 4.2 Endpoints

In **Protocol 1**, the primary and secondary outcomes from the original grant were updated after interruption from the COVID-19 pandemic shut-downs led to not being able to collect originally planned Aim 2 outcomes: MSNA; FMD;  $\beta$ -stiffness index; Wall thickness, Dynamic arterial compliance; Reactive hyperemia; and Baroreflex sensitivity. In **Protocol 2**, The primary cognitive outcome is a memory domain composite score calculated as the average of age-corrected list-sorting and age-corrected picture sequence z scores. The primary brain biomarker of ADRD risk outcomes are arterial transit time variables mean perfusion in gray matter and mean

perfusion in white matter. The primary and secondary outcomes are shown by protocol and aim in **Table 1** below.

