**Table 1. Outcomes by Protocol and Aim**

Protocol 1			
Outcomes	Aim 1	Aim 2	Aim 3
Primary	Clinic systolic and diastolic pressures; Ambulatory systolic and diastolic pressures	Pulse Wave Velocity (measure of arterial stiffness)	Acute and chronic pressure reductions
Secondary	Heart rate; Cardiac output; Stroke volume; Total peripheral resistance; Secondary BP outcomes: waking, sleeping, dipper vs. non-dipper	Blood-borne biomarkers	
Protocol 2			
	Cognitive	Brain biomarkers of ADRD risk	
Primary Outcomes	Memory domain composite score*	Arterial transit time: mean perfusion in gray matter, mean perfusion in white matter	

\*average of age-corrected list-sorting and age-corrected picture sequence z-scores

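### The statement that powering for blood pressure gives adequate power for the other cardiovascular measurements rests only on effect sizes for outcomes that could not be collected

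*SAP*

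**What the plan says.** SAP section 6 derives the blood pressure effect sizes from assumed between-arm differences in the fall of 4.0, 4.5 and 5.0 mmHg, "using a SD of 4.5 mmHg from our pilot work and published studies using similar interventions and approaches". Dividing gives its three Aim 1 values: 0.89, 1.00 and 1.11. It then lists effect sizes for six other outcomes: MSNA 1.43, beta-stiffness 1.43, DAC 1.70, sympathetic baroreflex 1.33, FMD 2.55 and carotid wall thickness 3.33. From these it concludes: "Effect sizes for blood pressures were the lowest of our outcome variables; thus, powering for blood pressure will allow adequate power for numerous measurements". The next paragraph describes 0.89 as the smallest effect of interest over all outcomes.

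Protocol section C (projected effect sizes and statistical power) keeps the same conclusion, "powering for blood pressure will allow adequate power for numerous measurements giving us a global picture cardiovascular and autonomic health", and the same description of 0.89. It lists no effect size other than those for blood pressure.

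SAP 4.2 reports that the pandemic shut-downs "led to not being able to collect originally planned Aim 2 outcomes". It names MSNA, FMD, beta-stiffness index, wall thickness, dynamic arterial compliance, reactive hyperemia and baroreflex sensitivity. Table 1 then gives the Aim 2 primary outcome as "Pulse Wave Velocity (measure of arterial stiffness)", with blood-borne biomarkers as secondary. Heart rate, cardiac output, stroke volume and total peripheral resistance are Aim 1 secondaries.

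**The concern.** SAP 4.2 was updated when the outcomes were lost, and section 6 was not. The ranking that puts blood pressure lowest now compares it only with measurements that could not be made. Pulse wave velocity carries the Aim 2 hypothesis that heat improves arterial stiffness more than exercise does, yet it has no effect size in either document.

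What is at stake is how a null Aim 2 result is read. If the sentence stands, a reader may take a non-significant group-by-time interaction for pulse wave velocity or a biomarker as the outcome of an adequately powered test, and so as evidence of no difference between heat and exercise.

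**Working it through.** **1. The plan's effect sizes reproduce.** Blood pressure: 4.0/4.5 = 0.89, 4.5/4.5 = 1.00, 5.0/4.5 = 1.11. MSNA: (39 − 29)/7 = 1.43.

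**2. Match against the uncollected list.** This reads DAC as dynamic arterial compliance (SAP section 2 does not define it) and sympathetic baroreflex as baroreflex sensitivity.

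| Effect size in SAP 6 | Value | Uncollected per SAP 4.2 |
|---|---|---|
| MSNA | 1.43 | yes |
| Beta-stiffness | 1.43 | yes |
| DAC | 1.70 | yes |
| Sympathetic baroreflex | 1.33 | yes |
| FMD | 2.55 | yes |
| Carotid wall thickness | 3.33 | yes |

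Six of six are on the list. The count of effect sizes for pulse wave velocity, the biomarkers or the haemodynamic secondaries is zero in both documents.

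**3. Is the ranking like for like?** The blood pressure d is a between-arm difference in change. The MSNA d, the only other one worked out, is a pre-to-post change. Its baseline of 39±7 is "based on our pilot data with 4 HTN subjects", and its post value of 29 was chosen because it "would represent a clinically significant change (of 10 b/100bts)". A within-group change does not give the heat-versus-exercise contrast, because exercise may also move the outcome. For the other five values the SAP does not say which kind of difference was used.

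**4. What the sample can detect.** Inputs: the plan's two-sample t-test, alpha 0.05 taken as two-sided (the plan does not state sidedness), 40 completers (20 per arm) or all 50 (25 per arm). The normal approximation is d = (1.96 + z_power) × √(2/n). With n = 20 it gives 2.80 × 0.316 = 0.89 at 80% power and 3.24 × 0.316 = 1.03 at 90%. The exact noncentral-t values are slightly larger:

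| Per arm | d for 80% power | d for 90% power |
|---|---|---|
| 20 | 0.91 | 1.05 |
| 25 | 0.81 | 0.94 |

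**5. Power over a range of d.** With 20 per arm, power is 98% at d = 1.33, the smallest of the six. So the inference to adequate power followed for the uncollected outcomes, if their d values are taken as between-arm. For a retained outcome any d is an assumption: 0.5 gives 34% (41% with 25 per arm), and 0.7 gives 58% (68%).

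**6. Consistency with the stated power.** Under the normal approximation at d = 0.89, power is Φ(0.89 × √(n/2) − 1.96). With n = 20 this is Φ(2.81 − 1.96) = 80%; with n = 25 it is Φ(3.15 − 1.96) = 88%. The t-test gives 78% and 87%. The plan states 90%. A one-sided test gives 87% with 40 and 93% with 50. The detectable values in step 4 therefore cannot be printed beside the present 90% statement without reconciling the two.

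**The case against.** - **The sentence does not name pulse wave velocity.** It speaks of numerous measurements, so the claim reaches pulse wave velocity by implication only. That stands. But pulse wave velocity is the sole Aim 2 primary outcome, and a reader will apply the sentence to it.
- **Beta-stiffness and DAC are related arterial measures.** They are relevant pilot information, but they do not supply an effect size for pulse wave velocity.
- **The study is described as hypothesis-generating (SAP 7.5), and estimated effects are already among the planned tables.** Both are true and both limit the harm. Neither supports the adequacy claim, and the first sits awkwardly beside it. The table list does not mention confidence intervals.
- **The t-test is a simplification.** SAP section 9 plans a three-timepoint mixed model, so the detectable values are indicative. They use the model the plan itself chose for its power statement.
- **Section 6 records how the size was set prospectively.** This is fair. It is a reason to label the six values rather than delete them.

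Three stronger readings are tempting, and the documents support none of them. A reader might infer that the retained outcomes are underpowered, but with no effect size given their power cannot be computed either way. A reader might extend the claim to Protocol 2, but the sentence is confined to cardiovascular and autonomic health, and Protocol section C ties the Protocol 2 size of up to 40 to one year of extra funding. A reader might take the MSNA figure as a change seen in four people, but only the baseline came from them.

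**Conclusion.** The point holds as a gap in justification. The statements that blood pressure has the lowest effect size, and that power is therefore adequate for the other measurements, have no support for the outcomes now in Table 1. All six comparison values are for uncollected outcomes, and the one that is worked out is not comparable with the blood pressure figure. The sample gives 80% power only for between-arm differences of about 0.8 to 0.9 SD, and 90% only for about 0.9 to 1.05 SD. This assumes a two-sided 5% t-test, equal arms, and 40 to 50 analysed. Whether the retained outcomes have effects that large is not stated. The sample size and the planned analyses do not depend on this point; what a null Aim 2 result can be said to show does.

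**What to change.** 1. In both documents, delete the sentence ranking blood pressure lowest and claiming adequate power, and the phrase calling 0.89 the smallest effect of interest over all outcomes.
2. In the SAP, mark the six effect sizes as belonging to the original outcomes that were not collected.
3. State that the size was set for blood pressure only, and that pulse wave velocity, the biomarkers and the haemodynamic secondaries were not separately powered. Give the detectable differences: 0.91 and 1.05 (80% and 90% power) with 20 per arm, 0.81 and 0.94 with 25 per arm.
4. Reconcile these with the stated 90% power at 0.89, which computes to 78% with 40 completers and 87% with 50, and state the sidedness of alpha.
5. Report these outcomes as between-arm estimates with 95% confidence intervals, and do not read non-significance as no difference.
6. If Protocol 2 is mentioned, say only that its size of up to 40 was set by funding and not by power. If the same 20% dropout is assumed, 40 × 0.8 = 32, or 16 per arm, and the detectable d is 1.02 (80%) or 1.19 (90%).

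The cost is wording in two documents and a less favourable power statement. No extra patients are needed.
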